At that point, patients initially randomized to Arm A who develop disease progression and who remain eligible for trial therapy based upon the trial inclusion/exclusion criteria will be given the

option of receiving additional experimental therapy with trametinib and GSK2141795. This option will not be available to patients who are taken off treatment due to the development of unacceptable toxicity that is not manageable with dose reduction. This will provide, in an exploratory fashion, information about the ability of AKT inhibition with GSK2141795 to salvage progression to trametinib. Tumor response assessments and progression-free survival will be recorded, but these patients will not be included in analysis of the primary analysis of PFS after first randomization; however, clinical outcome will be followed and reported in a descriptive fashion.

Pre-treatment paraffin embedded tissue will be collected from all patients at baseline for Gnaq/11 molecular analysis, with additional tissue stored for the future conduct of additional correlative studies. All patients with safely accessible tumor will undergo pre- and post-treatment (day 14 +/- 3 days) tumor biopsies for biomarker and correlative analysis. The decision to not pursue these biopsies must be made in collaboration with the MSK Principal Investigator. An additional tumor biopsy will be requested from patients at the time of disease progression; however, this biopsy is optional. Blood samples will be collected from all patients at baseline and on a monthly basis for correlative analysis.

As of 11/06/2015, Arm B met the specified stopping rule for futility. The remaining patients will be accrued to Arm A, no patients will be enrolled to Arm B or Crossover therapy.

TABLE OF CONTENTS

1	OBJECTIVES	10
	1.1 Primary Objectives.....	10
	1.2 Secondary Objectives.....	10
	1.3 Exploratory Objectives	10
2	BACKGROUND	10
	2.1 Uveal Melanoma.....	10
	2.2 CTEP IND Agents	11
	2.3 Study Rationale.....	22
	2.4 Correlative Studies Background	28
3	PATIENT SELECTION	30
	3.1 Inclusion Criteria	30
	3.2 Exclusion Criteria	32
	3.3 Eligibility Criteria for Crossover Registrations	34
	3.4 Inclusion of Women and Minorities	34
4	REGISTRATION PROCEDURES	35
	4.1 Investigator Registration.....	35
	4.2 MSK Research Participant Registration Procedures.....	35
	4.3 Participating Sites Research Participant Registration Process.....	35
	4.4 Randomization	36
	4.5 Crossover	37
5	TREATMENT PLAN.....	37

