As U0126, a non-specific inhibitor of MEK at micromolar concentrations, has been shown to inhibit the growth of Gnaq mut melanoma cell lines in prior studies, we evaluated if a similar effect could be achieved with selumetinib, a clinically available MEK inhibitor.⁵¹ We obtained and/or developed our own UM cell lines of differing genetic backgrounds. We treated cells with increasing concentrations of selumetinib and analyzed cell viability after 3 days of continuous drug exposure in the Dojindo cell based assay. Gnaq wild-type cells were resistant to increasing concentrations of selumetinib (see figure [below](#)) BRAF mutant cell lines tended to be more sensitive to the drug (IC50s <50nM), but Gnaq/11 mutant cell lines still exhibited a high degree of sensitivity, with IC50s between 100-250nM.

[figure not shown]

As shown by western blot (see figure [below](#)), this sensitivity correlated to the degree of p-ERK inhibition at 24 hours. Thus, the decrease in cell viability of Gnaq mut cell lines to selumetinib is dose dependent, associated with sustained inhibition of pERK at 24 hours, and comparable to that observed in BRAF mutant UM cell lines at clinically achievable drug concentrations.

2.3.3 Clinical Efficacy of Selumetinib in Patients with Advanced Uveal Melanoma.

Based upon this preclinical as well as preliminary clinical evidence of activity of selumetinib in advanced uveal melanoma,⁵² we developed and are conducting a CTEP sponsored trial entitled, “A Randomized Phase II Trial of Temozolomide versus selumetinib in Patients with Metastatic Uveal Melanoma (NCI#8443).” As presented at the 2013 American Society of Clinical Oncology Annual Meeting (see figure [below](#)), 7 of 46 patients initially randomized to selumetinib, achieved a RECIST partial response (15%), with half of the patients treated achieving radiographic shrinkage.⁵³ The response rate of those randomized to temozolomide/DTIC is 0%.

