A total of 98 patients have been randomized to selumetinib (n=48) and temozolomide/DTIC (n=50). Randomization was balanced by age, gender, performance status, stage and prior therapies. Greater than 90% of patients on both arms had metastatic liver disease. The primary endpoint of this study was progression-free survival, with secondary endpoints including overall survival and safety/toxicity. As of April 22, 2013, 44 patients initially randomized to chemotherapy have experienced radiographic progression, with 3 patients having experienced clinical progression. Thirty-four patients initially randomized to selumetinib experienced radiographic progression, with 2 having clinical progression. The study met its primary endpoint of PFS, with a median PFS of 15.9 weeks (95% CI, 8.4 – 23.1) with selumetinib

[figure not shown]
versus 7.0 weeks (95% CI, 4.3 – 8.4) with chemotherapy. The hazard ratio was 0.46 (95% CI, .30 - .71) with a p value of 0.0005). Despite the crossover design of the trial, with 80% of patients crossing over from chemotherapy to selumetinib, there was a trend towards improved survival with selumetinib (10.8 months versus 9.4 months; HR 0.79; p = 0.4).

2.3.4 Pharmacodynamic Activity of Selumetinib in Uveal Melanoma.

As part of this trial, we are collecting fresh tumor biopsies at baseline and after 14 days of treatment in patients treated at MSK with selumetinib. We have thus far successfully collected paired samples from 28 patients.

In our analysis of the first 18 patients treated with selumetinib from whom we have obtained paired tumor biopsies, we observed that the median pERK and cyclinD1 as measured by densitometry decreased by 48% (p=.03) and 76% (p=.03), respectively.⁵⁴ Radiographic regression correlated with suppression of pERK (p=0.04), but not cyclinD1 (p=0.38) in this sample set. Patients achieving clinical benefit as defined as having either a RECIST response or disease stability of 16 weeks or greater had a greater decline in median pERK (81.4%, interquartile range 58% to 96%) versus those not achieving clinical benefit (26.6%, interquartile range 11% to 60%), suggesting that more potent inhibition of the MAPK pathway may result in greater clinical benefit.

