9.4.2 Assessment of Pharmacodynamic Effects of Therapy

Patients with accessible tumor will undergo pre- and post-treatment (day 14 +/- 3 days) tumor biopsies for pharmacodynamic analysis. Studies which may include, but are not limited to, reverse phase protein array and Western blotting may be performed on serial tumor samples obtained from patients treated with trametinib alone and with the combination of trametinib and GSK2141795 for pERK, pAKT, cyclin D1, and others. Changes in protein levels will be semi-quantified by densitometry. We anticipate inhibition of pERK and cyclin D1 and

induction of pAKT with trametinib alone, and inhibition of pERK, cyclin D1, and pAKT with combination therapy.

RNA-seq will be performed using pre- and post-treatment material obtained from 5 patients achieving clinical benefit and 5 patients not achieving clinical benefit on each treatment arm. Clinical benefit is defined as a RECIST response or progression-free survival greater than 16 weeks. From our computations,⁶⁴ in order to identify 90% of differentially expressed genes between two conditions (with fold-changes=2 and FDR=0.05), 4 replicates per condition would be required. However, taking in account the inherent variability of biological samples, our power calculations suggest that 5 biological replicates per condition will be sufficient to identify 85-90% of differentially expressed (DE) genes. Our interim analysis of patients treated with selumetinib on NCI Protocol #8443 demonstrated a 40% clinical benefit rate. Assuming a similar clinical benefit rate for patients treated with trametinib alone and a clinical benefit rate of 60% for patients treated with trametinib and GSK2141795, we would predict that for every 13 patients, there will be at least 5 who achieve clinical benefit and 5 who do not. As the true clinical benefit rate for each arm is not known, we will perform paired biopsies on the first 15 patients treated on each arm.

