13.5 Analysis of Exploratory Endpoints

For patients who progress on trametinib and crossover to the combination arm clinical outcomes will be summarized. Response rate (CR+PR) will be estimated along with progression-free and overall survival from the start of combination therapy. Toxicity for the crossover patients will be reported by type, frequency and severity according to the NCI Common Toxicity Criteria.

Clinical response will be associated with Gnaq/11 mutational status using Wilcoxon rank sum test. An additional exploratory objective is to assess whether circulating tumor DNA can be detected. If so, these numeric data will be summarized by clinical response.

Using the 30 or more paired tumor biopsies collected on this study, associations between suppression specifically of p-ERK, AKT, Cyclin-D1, and response to treatment will be assessed using Fisher's exact test. Baseline and post-treatment status as well as changes will be reported. Assessment of apoptosis in the paired samples will be performed by caspase3 cleavage; changes will be assessed by a Wilcoxon signed rank test. These correlative studies will be considered exploratory in nature.

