13.6.2 Evaluation of Response

All patients included in the study must be assessed for response to treatment, even if there are major protocol treatment deviations or if they are ineligible. Each patient will be assigned one of the following categories: 1) complete response, 2) partial response, 3) stable disease, 4) progressive disease, 5) early death from malignant disease, 6) early death from toxicity, 7) early death because of other cause, or 9) unknown (not assessable, insufficient data). [Note: By arbitrary convention, category 9 usually designates the "unknown" status of any type of data in a clinical database.]

Intent-to-treat analysis will be performed in all who were randomized and who received at least one dose of study treatment in the main analysis of PFS (evaluable population). Patients in response categories 4-8 should be considered to have a treatment failure (disease progression). Thus, an incorrect treatment schedule or drug administration does not result in exclusion from the analysis of the response rate.

All conclusions should be based on all eligible patients. Subanalyses may then be performed on the basis of a subset of patients, excluding those for whom major protocol deviations have been identified (*e.g.*, early death due to other reasons, early discontinuation of treatment, major protocol violations, etc.). However, these subanalyses may not serve as the basis for drawing

conclusions concerning treatment efficacy, and the reasons for excluding patients from the analysis should be clearly reported. The 95% confidence intervals will be provided.

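### Section 13.5 tests marker suppression against response with a pooled Fisher's exact test and no cut-off; an arm-stratified rank-sum test would use the measured change at almost no cost

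*Combined protocol and SAP*

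**What the plan says.** Section 13.5 uses at least 30 paired biopsies and states that "associations between suppression specifically of p-ERK, AKT, Cyclin-D1, and response to treatment will be assessed using Fisher's exact test". It says that status and changes will both be reported, and it calls the correlative work exploratory. No significance level, power or separation by arm is given for this test. In the same section, the caspase-3 change is tested with a Wilcoxon signed rank test, and mutation status against clinical response with a rank-sum test.

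Section 9.4.2 describes the measurement: "Changes in protein levels will be semi-quantified by densitometry". It expects pERK and cyclin D1 to fall on trametinib alone, with "induction of pAKT with trametinib alone, and inhibition of pERK, cyclin D1, and pAKT with combination therapy". It also says that "Clinical benefit is defined as a RECIST response or progression-free survival greater than 16 weeks", and it assumes benefit rates of 40% on trametinib alone and 60% on the combination.

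The Fisher sentence does not say what response means. Sections 13.4 and 13.5 gloss response rate as CR+PR. Section 9.4.2 gives clinical benefit its own name. Section 13.6.2 uses a longer list: "Each patient will be assigned one of the following categories: 1) complete response, 2) partial response, 3) stable disease, 4) progressive disease", and further categories after that.

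On the source of the samples, the Schema says: "All patients with safely accessible tumor will undergo pre- and post-treatment (day 14 +/- 3 days) tumor biopsies".

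**The concern.** Fisher's exact test needs each patient classed as suppressed or not suppressed. The plan measures a graded change and never defines the class, so the test cannot be run until someone picks a threshold. Two things follow. The size of the fall, which is what the biopsies were taken to measure, drops out of the test. The result also depends on a choice that could be made after the data are seen.

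Pooling the arms raises a further problem for AKT. If the treatment moves the marker up in one arm and down in the other, a pooled analysis places most of one arm above any cut and most of the other below it. A relation with response inside each arm is then hard to see.

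What is at stake is one exploratory question: whether suppressing the target goes with response. Finding markers of sensitivity and primary resistance is a stated exploratory objective (Section 1.3), and patients undergo paired biopsies to supply the data.

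**Working it through.** **1. The plan's own number.** Section 9.4.2 plans pairs from the first 15 patients on each arm: 15 x 2 = 30, which agrees with Section 13.5. The plan gives no power for this test, so there is none to reproduce.

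**2. Inputs.**
- Responders, RECIST reading: Section 2.3.3 reports 7 of 46 (15%) on selumetinib; 0.15 x 30 = 4.5, taken as 5 v 25.
- Responders, clinical-benefit reading: 0.40 x 30 = 12, so 12 v 18. The combination's assumed 60% would give 6 + 9 = 15.
- pERK decline (Section 2.3.4, selumetinib, by clinical benefit): median 81.4% (IQR 58 to 96) v 26.6% (IQR 11 to 60).
- Assumed, because the documents give nothing: two-sided 5%; a normal shift of 1.0 SD; Fisher cuts at the median, the top third and the top two-thirds of the change, and at 30, 50 and 70% decline for pERK; quartile-curve ends of 0 to 100 (benefit) and -50 to 100 (no benefit).

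**3. Why the cut matters, by hand.** With 5 responders among 30 and m patients called suppressed, P(X = x) = C(m,x) C(30-m,5-x) / C(30,5), where C(30,5) = 142,506.
- m = 15: all 5 suppressed has probability 3,003/142,506 = 0.021, two-sided p = 0.042. Four of 5 gives p = 0.33.
- m = 10: 4 of 5 gives (4,200 + 252)/142,506, p = 0.031.
- m = 20: even 5 of 5 gives (15,504 + 4,200 + 252)/142,506, p = 0.14.

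At the top-two-thirds cut the test therefore cannot reach 5% in the expected direction. That is why its power is 0%.

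**4. Power by simulation, 30 pairs.**

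| Setting | Rank-sum | Fisher, over cuts |
|---|---|---|
| RECIST response, 5 v 25, 1.0 SD | about 46% | 30-41%; 0% at top two-thirds |
| Clinical benefit, 12 v 18, 1.0 SD | 70% | 27-54% |
| Clinical benefit, 0.8 SD | 52% | 17-38% |
| Clinical benefit, 1.25 SD | 88% | 47-74% |
| pERK quartiles, clinical benefit, 12 v 18 | 85% | 46-70% |
| pERK quartiles, RECIST response, 5 v 25 | about 30% | 5-29% |

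In the last row, 12 - 5 = 7 of the 25 non-responders have clinical benefit without a RECIST response, so they carry the benefit distribution and blur the contrast. A top-two-thirds cut again gives about 0% there, for the reason in step 3. With no association, Fisher at the median rejects 4.2% (5 v 25) and 0.8% (12 v 18), and the rank-sum test 5.0% and 4.5%.

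A second simulation drew responders at random at 40% and 60% by arm and used a shorter lower tail for patients without benefit (-20). On the pERK data it gave Fisher 55-63%, arm-stratified rank-sum 81% and unstratified rank-sum 84%.

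**5. AKT and arm.** Value = standard normal + 1.0 x response + gap x arm, with 15 patients and 6 responders per arm. The stratified statistic is T = sum over arms of [W - k(n+1)/2]/(n+1), where W is the responders' rank sum, k the responders and n the patients in that arm. At an assumed gap of 2 SD: pooled Fisher 4-21% depending on the cut, pooled rank-sum 34%, stratified rank-sum 70%. At gap 0: pooled rank-sum 71%, stratified 69%.

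**6. False positives from arm, no relation within arm.** With 6 v 9 of 15 responders (the protocol's 40% and 60%) and gaps of 1 to 3 SD, pooled Fisher rejects at most about 2-3%. With responders drawn at random at those rates and an 80-point marker shift, it rejects 6-8% (3-10% over shifts of 50 to 100 points). The stratified test stays at about 5%.

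**The case against.** **Suppression may be meant as a category.** Section 9.4.2 says only that such assays may be done and calls the result semi-quantified. Section 9.2.1 assigns some tissue to immunohistochemistry, Section 13.5 mentions status, and Section 2.3.4 speaks of no suppression in some patients. This is a fair reading, and Fisher's test would then fit. What remains is that no category is defined. A rank test also handles ordinal scores, so it is safe under either reading. The changes will be reported in any case, so the loss is confined to this test.

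**Response most naturally means CR+PR, where the gain is smaller.** This stands. At good cuts on the mixed pERK data the two tests are nearly level (about 30% v 26-29%), and with 3 responders they can tie (30% each at the top-third cut). A reader might infer from the clinical-benefit figures, such as 70% against 27%, that the planned test loses more than half its power. The documents do not support that as a general statement: it needs clinical benefit as the outcome and Fisher's worst cut.

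**A reader might infer that pooling makes the planned test produce false findings.** The documents do not support that either. A pooled rank-sum test rejects 29% of the time with 9 v 3 of 15 responders and a 2 SD gap, but the plan does not use that test and nothing in the protocol suggests that split. At the protocol's own rates, Fisher is near or below its nominal level in most settings.

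**Arm B may add little.** Arm B met the futility rule, which is zero or one RECIST response among 20. This also stands: under CR+PR its stratum would carry little information.

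**Conclusion.** The point holds as a modest one about efficiency and pre-specification. The planned test is not invalid. It cannot be run as written without a cut-off that the plan omits, it discards the size of the change, and its power varies widely with the cut. The cost is clearest if clinical benefit is the outcome, and for AKT if the arms differ as Section 9.4.2 expects. It is small if response is CR+PR and the cut happens to be well placed.

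The sizes rest on an assumed two-sided 5% level, assumed shifts and tails, selumetinib data for pERK only, and an arm gap of 2 SD that has no source in the documents. The direction is steadier than the sizes: the rank-sum test was ahead of or level with Fisher in nearly every setting examined with a real effect and comparable arms. The primary PFS comparison, the sample size and patient care are unaffected. This is a cheap improvement of low severity.

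**What to change.** In Section 13.5, replace the Fisher sentence with text to this effect:

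- The change from baseline to day 14 in p-ERK, AKT and Cyclin-D1 will be compared between responders and non-responders with an exact Wilcoxon rank-sum test stratified by treatment arm (van Elteren). Results will also be shown by arm.
- Response is RECIST CR+PR (or, if that is what is intended, the clinical benefit of Section 9.4.2).
- Fisher's exact test is supportive, with the suppression cut-off fixed before assay results are linked to response.
- With fewer than about 5 responders, results are reported descriptively.

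The cost is a few sentences, with no added samples, assays or patients. Stratifying gives up a little power if the arms do not differ: 69% v 71% with 6 + 6 responders, and 41% v 48% with 4 + 1. The second case is the closer one if Arm B has at most one responder. The simple suppressed/not-suppressed table becomes a supporting display.

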13.6 Reporting and Exclusions

13.6.1 Evaluation of Toxicity

All patients will be evaluable for toxicity from the time of their first treatment with trametinib and GSK2141795.

13.6.2 Evaluation of Response

All patients included in the study must be assessed for response to treatment, even if there are major protocol treatment deviations or if they are ineligible. Each patient will be assigned one of the following categories: 1) complete response, 2) partial response, 3) stable disease, 4) progressive disease, 5) early death from malignant disease, 6) early death from toxicity, 7) early death because of other cause, or 9) unknown (not assessable, insufficient data). [Note: By arbitrary convention, category 9 usually designates the "unknown" status of any type of data in a clinical database.]

Intent-to-treat analysis will be performed in all who were randomized and who received at least one dose of study treatment in the main analysis of PFS (evaluable population). Patients in response categories 4-8 should be considered to have a treatment failure (disease progression). Thus, an incorrect treatment schedule or drug administration does not result in exclusion from the analysis of the response rate.

All conclusions should be based on all eligible patients. Subanalyses may then be performed on the basis of a subset of patients, excluding those for whom major protocol deviations have been identified (*e.g.*, early death due to other reasons, early discontinuation of treatment, major protocol violations, etc.). However, these subanalyses may not serve as the basis for drawing

conclusions concerning treatment efficacy, and the reasons for excluding patients from the analysis should be clearly reported. The 95% confidence intervals will be provided.

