11.1.1 Definitions

Evaluable for toxicity. All patients will be evaluable for toxicity from the time of their first treatment with trametinib alone or with GSK2141795.

Evaluable for objective response. Only those patients who have measurable disease present at baseline, have received at least one cycle of therapy, and have had their disease re-evaluated will be considered evaluable for response. These patients will have their response classified according to the definitions stated [below](#). (Note: Patients who exhibit objective disease progression prior to the end of cycle 1 will also be considered evaluable.)

Evaluable Non-Target Disease Response. Patients who have lesions present at baseline that are evaluable but do not meet the definitions of measurable disease, have received at least one cycle of therapy, and have had their disease re-evaluated will be considered evaluable for non-target disease. The response assessment is based on the presence, absence, or unequivocal progression of the lesions.

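### The main PFS set is labelled intent-to-treat but requires a dose, Section 11.1.6 starts PFS at a different date from 13.1, and the response denominator is not reconciled across 13.6.2, 11.1.1 and 13.4

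*Combined protocol and SAP*

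**What the plan says.** **PFS population.** Section 13.6.2 states: "Intent-to-treat analysis will be performed in all who were randomized and who received at least one dose of study treatment". It applies this to the main PFS analysis and calls the same patients the evaluable population.

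**PFS start date.** Section 13.1 measures PFS from randomisation and says so twice. The schema and Section 5.1 also speak of PFS after first randomisation. Section 11.1.6 defines PFS from the start of treatment.

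**Response population.** Three rules appear:
- Section 13.6.2 opens with "All patients included in the study must be assessed for response to treatment, even if there are major protocol treatment deviations", and extends this to ineligible patients.
- The same section later says: "All conclusions should be based on all eligible patients".
- Section 11.1.1 limits evaluability for response: "Only those patients who have measurable disease present at baseline, have received at least one cycle of therapy, and have had their disease re-evaluated". It adds that "Patients who exhibit objective disease progression prior to the end of cycle 1 will also be considered evaluable".

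Section 13.4 promises CR+PR by arm with a 95% confidence interval and names no denominator.

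**Failure rule.** Section 13.6.2 says "Patients in response categories 4-8 should be considered to have a treatment failure (disease progression". Its list runs from 1 to 7 and then gives 9 for unknown, so category 9 lies outside the rule.

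**Second stage.** Sections 4.4 and 5.1 record that from 11/06/2015 the remaining patients go to Arm A only. Section 13.1 will report a median PFS with a 95% interval for a continuing single arm, and leaves the second-stage plan to be settled with the sponsor.

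**The concern.** A set conditioned on receiving a dose is not intent-to-treat. Whether a patient starts treatment is decided after randomisation, and nothing in the protocol suggests that the arm is hidden at that point. Leaving out never-dosed patients can therefore unbalance the arms in a direction that cannot be known in advance.

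The two start dates affect both arms about equally, so they largely cancel in a comparison. They do not cancel in a single-arm median, which is what 13.1 reports once an arm has stopped.

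For response, the rate rises if patients who stop early without a re-evaluation, or whose response is unknown, are removed from the denominator. With several rules in the text and no order among them, the population, start date and denominator could be settled after results are known.

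**Working it through.** **1. The plan's own figure.** Inputs from 13.1: 76 events, hazard ratio 0.56, one-sided 5%, 1:1 allocation.

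Power = Φ(√76 × |ln 0.56| / 2 − 1.645) = Φ(8.718 × 0.2899 − 1.645) = Φ(0.882) = 81.1%.

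The plan states 80%, so the figure reproduces. The events needed for 80% are 74 by the Schoenfeld formula and 78 by Freedman's. If an assumed 2 to 4 of 80 patients were never dosed and events fell in proportion, there would be 76 × 78/80 ≈ 74 or 76 × 76/80 ≈ 72 events, with power 80.2% or 79.2%. Power is not the issue. The issue is which patients and which clock are used.

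**2. The rules side by side.**

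| Patient | 13.6.2, all included | 13.6.2, all eligible | 13.6.2, main PFS set | 11.1.1, response set |
|---|---|---|---|---|
| Randomised, eligible, never dosed, no further scan | in | in | out | out |
| Dosed, later found ineligible | in | out | in | in, if one cycle and re-evaluated |
| Eligible, dosed, stops in cycle 1, no re-evaluation and no objective progression | in | in | in | out |

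No two columns agree on all three rows. The eligible-patients rule differs from the PFS set in both directions: it keeps the first patient and drops the second.

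**3. Start date.** Suppose every patient starts treatment g weeks after randomisation and none progresses or dies in between. Each PFS time from randomisation is then g weeks longer than from first dose, and so is the median. The documents do not give g, but they limit it. Section 10 requires baseline evaluations within 14 days before treatment, with a 3-day scheduling tolerance. Section 4.4 randomises after eligibility is established, which needs the laboratory values in 3.1.9. Unless tests are repeated, g is therefore about 2 weeks at most. With the 16-week median of 13.1:
- g = 1: 16 + 1 = 17 weeks (1/16 = 6% longer)
- g = 2: 16 + 2 = 18 weeks (2/16 = 12.5% longer)

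**4. Response.** Take the 15% rate that Section 2.3.3 quotes for selumetinib: 0.15 × 40 = 6 responders in an arm of 40. Exact (Clopper-Pearson) 95% limits for x of n are the 2.5% point of Beta(x, n − x + 1) and the 97.5% point of Beta(x + 1, n − x).
- All 40 kept: 6/40 = 15.0% (5.7 to 29.8)
- An assumed 2 left out: 6/38 = 15.8% (6.0 to 31.3)

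If nobody is left out, nothing changes.

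**The case against.** **The plan does choose a response population.** The eligible-patients sentence can fairly be read as a choice, and the sentence on ineligible patients is strictly an instruction to assess them. Section 13.6.2 also keeps dosing errors in the response rate. Of subsets that drop early discontinuations and the like, it says "these subanalyses may not serve as the basis for drawing" conclusions on efficacy. A reader might infer that no denominator is chosen at all; that goes too far. What stands is that this partial choice is not reconciled with 11.1.1 or with the dosed PFS set, and 13.4 refers to none of them.

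**Unknowns stay in anyway.** Every included patient receives a category, so the natural reading keeps category 9 in the denominator as non-responders. That is likely, but the text does not say it.

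**The start date is settled.** Randomisation is clearly the better supported origin, and 11.1.6 is one line in the measurement section. For the arm comparison this is an editorial alignment.

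**Losses from the 11.1.1 set should be few.** Section 3.1.2 requires measurable disease of everyone, early objective progressors count as evaluable, and the study calendar continues scans every 8 weeks after a stop for other reasons. This is why the illustration uses only 2 of 40.

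**Arm B has closed.** The comparison is truncated, so the population rule matters less there. The Arm A median remains to be reported, however, and it is the quantity that the start date moves. The deferral in 13.1 is an open item, not a contradiction.

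**Conclusion.** The point holds and should be corrected. The intent-to-treat label is wrong for the set described, 11.1.6 conflicts with 13.1, and the response denominator is only partly chosen.

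The size is modest. The effect of leaving out never-dosed patients is of unknown direction and probably small. The start date moves a single-arm 16-week median by about 1 to 2 weeks, and the response rate moves by under one percentage point in the illustration. These sizes rest on an assumed gap and an assumed 2 of 40 left out; the documents give neither figure. Response is also secondary, and 13.4 calls it exploratory.

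Two stronger readings are tempting:
- A reader might take the 28-day biopsy window in 9.2.1 as a possible four-week delay, giving a 20-week median. That window limits the age of a biopsy, not the time from randomisation to first dose, and the 14-day baseline window in Section 10 is tighter.
- A reader might take the selumetinib arm, with 48 randomised and 46 counted for response (2.3.3) and n = 47 for median PFS (13.1), as proof that patients get dropped. That is another trial, described as still being conducted. The reasons are not given, and immature follow-up may explain them.

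**What to change.** 1. **Arm comparison.** Analyse any comparison of PFS between Arms A and B in all randomised patients as randomised, from the randomisation date. Keep the dosed set as a sensitivity analysis under its own name. Align 11.1.6 with 13.1.
2. **Response.** Use one primary denominator per arm: all randomised patients, plus later Arm A enrolees. Count anyone without a documented CR or PR, including category 9, as a non-responder. Make the 11.1.1 and eligible-only sets supportive, and reconcile the eligible-patients sentence with this.
3. **Second stage.** In the plan that 13.1 defers, state one inclusion rule and one clearly defined time origin for all Arm A patients. Registration date may look convenient because 4.4 links registration and randomisation, but 4.3 allows a PENDING registration with the completed checklist due up to 30 days after consent. A pending date should not start the clock. Show randomised and later directly assigned patients separately as well, and keep the later patients out of the arm comparison.

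The cost is wording, with no new data collection. The reported response rate may be slightly lower. Because the change follows the futility look, it should be dated and documented as such.
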